## BACKGROUND

Major depressive disorder (MDD) is a serious public health concern worldwide with ample documentation demonstrating that MDD is one of the leading contributors to the global burden of disease and is currently the leading cause of disability worldwide [1–3]. Moreover, the economic burden of MDD is estimated to total \$210.5 billion with approximately 50% of the cost being attributable to impairment in role function (e.g., workplace performance: presenteeism, absenteeism, and short-/long-term disability) [4,5]. Accumulating evidence suggests that the treatment and resolution of mood symptoms among individuals with MDD is insufficient in facilitating full functional recovery among individuals affected by MDD wherein a highly reproduced observation is that impairments in cognitive function remain persistent, pervasive, and progressive during the “remitted” state [6–8]. The foregoing portrait of MDD as a multidimensional syndrome associated with cognitive impairment and differential functional implications, provides the impetus for evaluating the disparate domains commonly affected in this clinical population using valid and reliable measures/assessments capable of providing actionable information in the treatment and management of patients.

Hitherto, clinical awareness surrounding the pertinence of cognitive impairment in MDD and its impact on functional recovery has been limited with no “gold standard tool(s)” to detect cognitive impairments in adults with MDD. Moreover, although several screening/measurement instruments are currently available that have demonstrated sensitivity to cognitive impairments in select cognitive domains, only one tool, to the authors’ knowledge, has been developed primarily to evaluate the four principal cognitive domains affected in adults (18-65) with MDD (i.e., executive function, learning and memory, processing speed, as well as attention/concentration) using a composite score.

The recently validated digitalized metric for assessing/screening cognitive deficits among adults

(18-65) with MDD - the THINC-integrated tool (THINC-it) - developed by the Global THINC Task Force, effectively demonstrated its ability to detect and measure cognitive performance. This tool is able to significantly differentiate between clinical (i.e., MDD) and healthy control populations based on measures of both objective and subjective cognition (McIntyre et al., 2017). The THINC-it is accessible via computers/tablets (downloadable, free of charge from the THINC-it website: <http://thinc.progress.im/en/form/download-thinc-it-tool>) and is comprised of the paradigms drawn from four objective measures of cognition: the Choice Reaction Time (CRT) (i.e., THINC-it: Spotter); the 0 N-BACK Working Memory Task (i.e., THINC-it: Symbol Check); the Digit Symbol Substitution Test (DSST) (i.e., THINC-it: Codebreaker); and the Trail Making Test- Part B (TMT-B) (i.e., THINC-it: Trails); in addition to the Perceived Deficits Questionnaire for Depression – 5 Item (PDQ-5-D) which assesses subjects' subjective experience of cognitive deficits.

The THINC-it was designed for patient self-administration in a clinical setting with no requirement for the tool to be delivered and/or scored by a psychometrist/psychologist. Patient results are made immediately available, taking approximately 30 minutes to complete. Instructions are conveyed in a manner that is commensurate with a grade 6 education and are not culture-bound. It is anticipated that the THINC-it tool will be available in the primary care and specialty setting in a digital format, providing actionable information for the treatment and management of patients with MDD.

The ideal gold standard tool for screening/assessing the presence of cognitive impairment in adults with MDD in the clinical ecosystem should include, but not be limited to, conceptual coverage of the cognitive domains affected in MDD (i.e., executive function, learning and memory, processing speed, and attention/concentration), validity and reliability, and minimal cultural/practice effects. The tool would also need to be brief and allow for easy administration and interpretation. Additionally, in order to make effective use of the information provided by the screening/assessment tool, it would also need to demonstrate sensitivity to change in cognitive function/performance following treatment. In keeping with this view, the objective herein is to establish sensitivity to change using THINC-it, as there is a need for an instrument

capable of tracking the progress of individuals receiving treatment for cognition dysfunction in MDD.

An 8-week, open-label, sensitivity to change study assessing alterations in cognitive function/performance, as measured by the THINC-it, in adults (18-65) with Diagnostic and Statistical Manual, Fifth Edition (DSM-5)-defined MDD treated with vortioxetine (10-20 mg flexibly dosed) is proposed. This study will be performed by the Brain and Cognition Discovery Foundation (BCDF). The BCDF is an organization based in Toronto, Ontario, Canada led by [name]. Membership of the BCDF has developed and validated rating scales and metrics for adults with mood disorders for over 10 years. A member of the BCDF provides diagnoses and treatment for adults (age 18-65) with mood disorders and provides clinical care to the largest catchment area in Canada. The BCDF conducts clinical research according to the International Conference on Harmonization, Declaration of Helsinki, and Good Clinical Practice (GCP) guidelines. The study will be approved by the community Research Ethics Board.

## **HYPOTHESIS**

The primary aim of this study is to establish sensitivity to change in cognitive function/performance using THINC-it tool in adults (18-65) with MDD treated with vortioxetine (10-20 mg flexibly dosed for 8 weeks). Secondary aims of the study include, but are not limited to: (1) determining whether early changes (i.e., Day 14; Week 2) in cognitive function/performance predict symptomatic improvements in mood (defined as a reduction of 50% or more on total mood score [as measured by the Montgomery Åsberg Depression Rating Scale [MADRS], at endpoint; and (2) determining whether early changes (i.e., Day 14; Week 2) in cognitive function/performance are capable of detecting the effect of vortioxetine treatment on secondary outcome measures assessing functional outcomes [e.g., Sheehan Disability Scale (SDS), Endicott Work Productivity Scale (EWPS), and the 5-Item World Health Organization Wellbeing Index (WHO-5)] at endpoint.

## STUDY DESIGN

This is an 8-week, open-label, sensitivity to change study assessing alterations in cognitive function/performance, as measured by the THINC-it, in adults (18-65) with Diagnostic and Statistical Manual, Fifth Edition (DSM-5)-defined MDD treated with vortioxetine (10-20 mg flexibly dosed) (N=100) and (N=50) age, and sex-matched, Healthy Controls.

## STUDY POPULATION

All patients will be enrolled at a single site, located in Toronto, Ontario, Canada.

The total planned number of participants is:

- ❑ 100 individuals with DSM-5-defined MDD (18-65 years of age)
- ❑ 50 Healthy Controls (18-65 years of age) matched on sex, and age

## ELIGIBILITY CRITERIA

The eligibility criteria provided below do not unnecessarily filter and/or restrict select patients.

The overarching aim of enrollment is to include representative patients to enhance the ecological validity of our results with careful consideration surrounding those patients likely to evince impairments/deficits in the dimension/domain of cognition. The rationale for the selection of those individuals with at least one prior major depressive episode (MDE), is based on extant literature indicating that individuals with recurrent MDD are at greater risk of inter-episodic “non-mood” symptoms including, but not limited to, cognitive impairments (e.g., indecision, difficulties with memory, and inability to concentrate) [8–11].

Similarly, the ideal participants would be antidepressant naïve and not receiving any psychotropic medication. However, the majority of patients with MDD seeking healthcare and/or utilizing healthcare systems have been prescribed and are taking at least one psychotropic medication including, but certainly not limited to, an antidepressant. Indeed, the possibility of

introducing potential confounds moderated by medication (i.e., iatrogenic artifacts) are raised when including patients taking antidepressants and/or other psychotropic/general medications; nonetheless, excluding patients currently receiving pharmacological treatment would significantly reduce the feasibility of a timely enrollment and would be liable to criticisms of non-representativeness. Therefore, participants would be evaluated by a study clinician on a case-by-case basis to determine the potential of pharmacodynamic interactions between the study intervention and the participant's current medication regimen as well as evaluating the likelihood of impacting study results.

Participants are advised to **NOT** use the THINC-it tool outside of the study, as to not affect study results during your participation.

***Inclusion Criteria for Participants with MDD:***

1. The participant is able and willing to provide informed consent.
2. The participant is male or female 18-65 years of age.
3. The participant has received a current diagnosis of a major depressive episode (MDE) as part of MDD as per DSM-5 criteria.
4. The participant's current MDE is confirmed by the Mini International Neuropsychiatric Interview (M.I.N.I 5.0.).
5. The participant is an outpatient of a psychiatric setting.
6. The participant has a MADRS score  $\geq 20$  at screening and baseline.
7. At least one prior MDE formally diagnosed by a healthcare provider or validated by previous treatment (e.g., guideline-informed pharmacotherapy and/or manual-based psychotherapy).

***Exclusion Criteria for Participants with MDD:***

1. Current alcohol and/or substance use disorder as confirmed by the M.I.N.I 5.0.
2. Presence of comorbid psychiatric disorder other than MDD that is a focus of clinical concern as confirmed by the M.I.N.I 5.0.
3. Medications approved and/or employed off-label for cognitive dysfunction

(e.g., psychostimulants).

4. Any medication for a general medical disorder that, in the opinion of the investigator, may affect cognitive function.
5. Use of benzodiazepines within 12 hours of cognitive assessments.
6. Consumption of alcohol within 8 hours of cognitive assessments.7 . Inconsistent use or abuse of marijuana.
8. Physical, cognitive, or language impairments sufficient to adversely affect data derived from cognitive assessments.
9. Diagnosed reading disability or dyslexia.
10. Clinically significant learning disorder by history.
11. Electroconvulsive therapy (ECT) in the last 6 months.
12. History of moderate or severe head trauma (e.g., loss of consciousness for >1 hour), other neurological disorders, or unstable systemic medical diseases that in the opinion of the investigator are likely to affect the central nervous system.
13. Pregnant and/or breastfeeding.
14. Received investigational agents as part of a separate study within 30 days of the screening visit.
15. Actively suicidal/presence of suicidal ideation or evaluated as being a suicide risk (as per clinical judgment using the Columbia-Suicide Severity Rating Scale).
16. Currently receiving treatment with Monoamine Oxidase Inhibitors (MAOIs) anti-depressants, antibiotics such as linezolid, or intravenous methylene blue.
17. Previous hypersensitivity reaction to vortioxetine or any components of the formulation.  
Angioedema has been reported in patients treated with vortioxetine.
18. Clinical worsening symptoms of depression and suicide risk – in both adult and pediatric age groups.
19. Serotonin syndrome
20. Abnormal bleeding

21. Previous history of mania/hypomania
22. Angle closure glaucoma
23. Hyponatremia
24. Moderate hepatic impairment
25. History of seizures and epilepsy

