## **Transition to Enrollment**

Patient will discontinue only antidepressants. Patients' existing antidepressant dosage will be decreased gradually over a course 10-14 days. At the same time, participants will be started on 10mg of Vortioxetine. It takes about 10-14 days for Vortioxetine to achieve steady states. For patients who are already taking antidepressants at the start of study, if they are abruptly discontinued, they are at risk for discontinuation syndrome. Therefore, both drugs will be co-prescribed for about 10-14 days and then the index antidepressant will be discontinued.

Serotonin syndrome or other additive side effects is very unlikely to be a concern. Should the patient's physician determine another optimal schedule, this will be followed instead. All MDD participants will be supervised by [name], prior to enrollment of the study. All patients will be monitored by a psychiatrist during the study. Furthermore, patients will have access to a 24-hour study number where they can contact research staff anytime, should they experience any adverse events. Therefore, there will always be an open line of communication between patients and the research staff.

The above mentioned procedures will only be carried out once participants have consented to take part in the research and signed the informed consent form.

Patients will be seen by a clinician on a biweekly basis for the antidepressant washout period. Clinician will be assessing the patient on adverse side effects, as well as mood.

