## **PROCEDURES FOR PARTICIPANTS WITH MAJOR DEPRESSIVE DISORDER**

### ***Visit 1 (Screening)***

The initial visit entails the provision of detailed study information to participant and obtainment

of informed written consent. A member of the research team will assess participants' eligibility based on inclusion/exclusion criteria and confirm a diagnosis of MDD with the M.I.N.I. 5.0 and the Structured Clinical Interview for DSM-5 (SCID) to assess for mixed features symptomatology. Demographics including date of birth, sex, and race will be recorded. Years of education will be recorded as well. Lifestyle factors (i.e. caffeine, exercise, alcohol, nicotine and marijuana ) will also be recorded. Psychiatric and medical history, number of psychotropic medications received according to participant self-report/clinical chart review, as well as anthropometrics (including height, weight and waist circumference) will be measured. Resting heart rate and blood pressure will also be measured. Participants will be evaluated with the MADRS by a member of the research team trained in MADRS scoring to assure the severity threshold is indicative of non-remission (MADRS  $\geq$  20). The Columbia Suicide Severity Rating Scale (CSSRS) will also be used as part of participant assessment. In addition, participants will be asked to report any experience of adverse event(s) prior to study enrollment. Participants will be asked to complete the NART to estimate premorbid intelligence quotient (IQ). Upon confirmation of study eligibility, the participant will be scheduled for future appointments.

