## Contraindications

Hypersensitivity to vortioxetine or any components of the formulation. Angioedema has been reported in patients treated with vortioxetine. The use of monoamine oxidase inhibitors (MAOI) intended to treat psychiatric disorders with vortioxetine or within 21 days of stopping treatment with vortioxetine is contraindicated because of an increased risk of serotonin syndrome. The use of vortioxetine within 14 days of stopping an MAOI intended to treat psychiatric disorders is also contraindicated.

Starting vortioxetine in a patient who is being treated with MAOIs such as linezolid or intravenous methylene blue is also contraindicated because of an increased risk of serotonin

syndrome.

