## Recordings of Adverse Events

Adverse events will be collected from baseline to endpoint. At each visit, subjects will be asked if they have experienced any health problems or side effects since the previous visit. All AEs will be recorded appropriately, whether or not considered related to the investigational product. This will include AEs spontaneously reported by the patient and/or observed by members of the research team as well as AEs reported in response to a direct question (e.g., “Have you experienced any health problems of side-effects since your last visit?”).

For each AE, the following parameters will be described:

- Start and Stop date
- Action taken with regards to investigational product
- Outcome
- If the AE caused the patient to discontinue the investigational product
- A statement if the AE fulfills the criteria for a SAE or not
- The investigator’s assessment of the causal relationship between the event and the investigational product
- Intensity of the AE
  - o Mild (awareness of sign or symptom, but easily tolerated)

- o Moderate (discomfort sufficient to cause interference with normal activities)
- o Severe (incapacitating, with inability to perform normal activities)

It is important to distinguish between serious and severe AEs. Severity is a measure of intensity. An AE of severe intensity need not necessarily be considered serious. For example, nausea that persists for several hours may be considered severe nausea, but not an SAE. On the other hand, a stroke that results in only a limited degree of disability may be considered a mild stroke but would be an SAE. Symptoms associated with overdose will be reported as AEs. Pregnancy in itself is not regarded as an AE. Follow-up of adverse events will be based upon the clinical judgment of the investigator.

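### Exclusion 16 bars only current MAOI use and omits the protocol's own 14-day interval after stopping a psychiatric MAOI

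*Combined protocol and SAP*

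**What the plan says.** **Eligibility.** In the exclusion criteria for participants with MDD, item 16 reads "Currently receiving treatment with Monoamine Oxidase Inhibitors (MAOIs) anti-depressants, antibiotics such as linezolid, or intravenous methylene blue". It is framed in the present tense and has no look-back. The same list does use look-backs elsewhere: six months for ECT, and for trial drugs "Received investigational agents as part of a separate study within 30 days of the screening visit".

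**Contraindications.** Under Study Medication, the protocol states: "The use of vortioxetine within 14 days of stopping an MAOI intended to treat psychiatric disorders is also contraindicated". The neighbouring sentences on MAOIs give serotonin syndrome as the reason.

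**Medication review, screening and switching.** The case-by-case clinician review under Eligibility Criteria is directed at the participant's "current medication regimen as well as evaluating the likelihood of impacting study results". Visit 1 takes psychiatric and medical history and the "number of psychotropic medications received according to participant self-report/clinical chart review". Transition to Enrollment describes the change from an existing antidepressant: "both drugs will be co-prescribed for about 10-14 days and then the index antidepressant will be discontinued".

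**Adverse events (secondary).** Recordings of Adverse Events states: "Adverse events will be collected from baseline to endpoint". The MDD Patient Summary Chart labels Week 8 as the endpoint and leaves the adverse event row blank in the post-study column. The general definition under Adverse Events, however, extends to washout periods.

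**The concern.** An exclusion list is what staff work through when they decide whether someone may enter. Here a patient who took a psychiatric MAOI until shortly before screening meets every written criterion on that drug, yet falls inside an interval in which the same protocol says vortioxetine must not be given. The eligibility rule and the dosing rule disagree, and the disagreement concerns a drug combination for which the protocol itself cites serotonin syndrome.

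What is at stake is the safety of an individual patient. The Week 8 THINC-it analysis is not affected.

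The secondary matter is one of record-keeping. Minor events that arise while the study drug is being withdrawn may be seen by a clinician but not entered as study data.

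**Working it through.** No statistical calculation applies. The check is a comparison of texts plus day counts.

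**1. Which contraindications reach the exclusion list?** Taking the items in Contraindications that matter before a first dose:

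- Hypersensitivity to vortioxetine or its components: carried by exclusion 17.
- Current MAOI treatment: carried by exclusion 16.
- Current linezolid or intravenous methylene blue: carried by exclusion 16.
- Psychiatric MAOI stopped less than 14 days earlier: not carried by any criterion.

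The 21-day interval in the same section concerns MAOIs taken after vortioxetine is stopped, so it is not an entry criterion. The look-back for psychiatric MAOIs is therefore 0 days in the list against 14 days in the contraindication.

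**2. Does another step state the interval?**

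- The case-by-case review is worded for current medication. A drug already stopped is outside that wording.
- Visit 1 mentions history and a medication count, but no stop date.
- The MDD chart has current medications at screening and medication changes from baseline onward. An MAOI stopped just before screening is neither.
- The inclusion/exclusion row of the chart is marked only at screening. The physician visit row starts at baseline.
- Transition to Enrollment sets an overlap of 10 to 14 days and gives no separate interval for MAOIs.

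None of these states 14 days.

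**3. How wide is the gap?** Let k be the days from last MAOI dose to screening (k of at least 1, since current users are excluded) and s the days from screening to first vortioxetine dose. The list misses a patient when k + s < 14. The protocol does not give s, so these values are assumptions:

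- s = 0: k < 14, so k = 1 to 13 are missed.
- s = 7: k < 7, so k = 1 to 6 are missed.
- s = 13: k < 1, so none are missed.

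If day 14 itself counts as within the interval, the condition becomes k + s ≤ 14. The ranges are then 1 to 14, 1 to 7, and k = 1 only. The number of patients in these ranges cannot be derived, because the protocol gives no frequency of recent MAOI use.

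**4. Secondary note on adverse events.** Collection ends at Day 56. For a tapered patient, one week at half dose and one week off drug end at Day 56 + 7 + 7 = 70. The stretch outside planned collection is 70 − 56 = 14 days per tapered patient. The number tapered is not given.

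**The case against.** The strongest reply is that the 14-day interval is already a rule of this protocol. Investigators are bound by the whole document, so what is missing from exclusion 16 is a repetition. Several steps also put medication history in front of a clinician: the history and chart review at Visit 1, the supervision of MDD participants before enrollment, monitoring by a psychiatrist, and the baseline physician visit. A protocol need not list every field on a case report form, so the absence of a named stop date proves little.

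Most of this stands, and it limits the conclusion. A reader might infer that the protocol permits dosing soon after an MAOI, or that nothing but the prescriber's memory of the contraindication stands in the way. The documents support neither reading. Nor does the 10 to 14 day overlap imply giving vortioxetine together with an MAOI, since exclusion 16 keeps current users out.

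What the reply does not answer is the mismatch itself. None of the safeguards states the interval, and the eligibility list should not pass a patient whom the protocol contraindicates for dosing. The gap between screening and baseline cannot be relied on as a washout, because its length is not specified.

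On adverse events, a reader might infer that patients go unobserved after Week 8. They do not. A physician visit about two weeks later already checks adverse events, a 24-hour phone line is open, and serious events are defined over any study phase, including washout and follow-up. Events still open at Week 8 may also be pursued: "Follow-up of adverse events will be based upon the clinical judgment of the investigator". The chart also marks adverse events at screening, before the stated baseline start, so the window sentence is not an exact boundary. What remains is an inconsistency between the definition and the collection window.

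**Conclusion.** The point holds as an omission from the eligibility rule. Exclusion 16 covers current MAOI use only, the protocol's contraindication extends 14 days after a psychiatric MAOI is stopped, and no eligibility, screening or switching text carries that interval. The list alone would pass a recent user; other parts of the protocol may still prevent dosing.

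Confidence in the text comparison is high. The number of patients is unknown and, as a judgement, probably small. The day ranges rest wholly on the assumed screening-to-baseline interval and on the list being applied at screening, where the chart marks it. The change is worth making because the possible harm is serious and the correction is nearly free.

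The adverse event window is a minor secondary note. It touches no stated objective.

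**What to change.** **Exclusion 16.** Add a clause excluding anyone whose last dose of an MAOI taken for a psychiatric indication fell within 14 days before the first dose of vortioxetine. Record the stop date of any such drug at screening and check it before the first dispensing at Visit 2. Tying the interval to the first dose, not to screening, makes the rule work whatever the gap between the two visits.

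Cost: one clause and one recorded date. A patient who has recently stopped such a drug waits out the remaining days or is not enrolled.

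**Adverse events (minor).** For patients who are tapered, extend collection to the clinician visit two weeks after Week 8 and mark the adverse event row of the MDD chart in that column. The discontinuation text can still call the visit clinical, provided it says that adverse events found there are entered in the study record.

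Cost: one further adverse event form per tapered patient, at a visit already planned. Neither change affects the Week 8 analysis.

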### ***Visit 2 (Day 0: Week 0; Baseline)***

Participant will be asked to report any adverse event(s) or any changes to medications. The Clinical Global Impression – Severity (CGI-S), MADRS, as well as the CSSRS scales will be used as part of participant assessment. Anthropometrics (including weight and waist circumference), resting heart rate and blood pressure will be measured. History of caffeine, alcohol, nicotine, exercise and marijuana use will be recorded as well. Participants will be provided with an opportunity to work through the modified THINC-it to minimize potential practice effects with a research team member. This will allow the participant with an opportunity to ask any outstanding questions. The THINC-it tool will be administered via tablet to evaluate objective and subjective measures of cognitive function. THINC-it tests will be consistently delivered in the following order: Spotter, Symbol Check, Codebreaker, Trails, and PDQ-5-D to all participants with a member of the research team instructing participants to read the tutorial

instructions preceding each of the THINC-it tasks. Participants will complete the pen-and-paper version of the Digit Symbol Substitution Test (DSST) and the Trail Making Test B (TMT-B).

Participants will also complete all secondary self-report assessments using paper-based scales/questionnaires and consist of the following scales: Endicott Workplace Productivity Scale (EWPS), Sheehan Disability Scale (SDS), Wellbeing Index (WHO-5), Snaith-Hamilton Pleasure Scale (SHAPS), Generalized Anxiety Disorder (GAD-7), Perceived Deficits Questionnaire for Depression (PDQ-5-D), International Physical Activity Questionnaire (IPAQ), 36-Item Short Form Survey Instrument (SF-36), Insomnia Severity Index (ISI), Pittsburgh Sleep Quality Index (PSQI), Epworth Sleepiness Scale (ESS) and THINC-it satisfaction questionnaire. All self reports will be administered by a member. All study procedures will take place in a quiet setting. Fasting (12-hours) clinical and research bloodwork will also be collected.

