### **MDD PATIENT SUMMARY CHART**

Visit	Screening (Visit 1)	Week 0 (Baseline, Visit 2)	Week 2 (Visit 3)	Week 4 (Visit 4)	Week 8 (Endpoint, Visit 5)	Post-Study two weeks clinical visit for drug discontinuation. Additional visits will be scheduled as needed.
Consent	X					
Physician visit		X	X	X	X	X
Bloodwork		X			X	
Demographics	X					
Inclusion/ exclusion	X					
Adverse events	X	X	X	X	X	
Current Medications	X					
Medication Changes		X	X	X	X	
M.I.N.I 5.0	X					
SCID	X					
Psychiatric/Medical History	X					
Anthropometrics	X	X	X	X	X	
Lifestyle Factors	X	X	X	X	X	
Montgomery Åsberg Depression Rating Scale (MADRS) > 20	X	X	X	X	X	
THINC-it Practice		X				
THINC-it Cognitive test		X	X		X	
CSSRS	X	X	X	X	X	
DSST (pen/paper)		X	X		X	
TMT-B (pen/paper)		X	X		X	
NART	X					
CGI-I/CGI-S		X	X	X	X	
International Physical Activity Questionnaire (IPAQ)		X		X	X	
Vortioxetine Treatment		X	X	X		
Dispensing medication		X	X	X		
Effort Expenditure for Rewards Task (EEfRT) – optional					X	

Endicott Workplace Productivity Scale (EWPS)		X	X		X	
Sheehan Disability Scale (SDS)		X	X		X	
Wellbeing Index (WHO-5)		X	X		X	
Snaith-Hamilton Pleasure Scale Questionnaire (SHAPS)		X	X		X	
Generalized Anxiety Disorder (GAD-7)		X	X		X	
Perceived Deficits Questionnaire for Depression (PDQ-5-D)		X	X		X	
36-Item Short Form Survey Instrument (SF-36)		X	X		X	
Insomnia Severity Index (ISI)		X	X		X	
Pittsburgh Sleep Quality Index (PSQI)		X	X		X	
Epworth Sleepiness Scale (ESS)		X	X		X	
THINC-it satisfaction questionnaire		X				

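### MAOI exclusion (item 16) covers current use only and omits the 14-day washout that the protocol's own Contraindications section requires

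*Combined protocol and SAP*

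**What the plan says.** The combined protocol and SAP deals with MAOIs in two places.

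- **Exclusion Criteria for Participants with MDD, item 16:** "Currently receiving treatment with Monoamine Oxidase Inhibitors (MAOIs) anti-depressants, antibiotics such as linezolid, or intravenous methylene blue".
- **Contraindications**, under the study medication: "The use of vortioxetine within 14 days of stopping an MAOI intended to treat psychiatric disorders is also contraindicated". For the two non-psychiatric agents the same section says: "Starting vortioxetine in a patient who is being treated with MAOIs such as linezolid or intravenous methylene blue is also contraindicated".

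The other steps that bear on prior medication are these.

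- **Eligibility Criteria:** a study clinician considers interactions case by case, looking at the participant's "current medication regimen as well as evaluating the likelihood of impacting study results".
- **Visit 1 (Screening):** psychiatric and medical history is taken, with the "number of psychotropic medications received according to participant self-report/clinical chart review".
- **Visit 2 (Baseline):** "Participant will be asked to report any adverse event(s) or any changes to medications".
- **MDD Patient Summary Chart:** the row "Inclusion/ exclusion" and the row for current medications are marked at screening only. A physician visit and the first dispensing are marked at Week 0.
- **Transition to Enrollment:** the existing antidepressant is tapered over 10 to 14 days while vortioxetine is started. No separate rule is given for MAOIs.

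**The concern.** The eligibility list and the Contraindications section define different sets of patients. Someone who has recently come off a psychiatric MAOI is no longer receiving it, so item 16 does not apply, yet dosing is contraindicated for 14 days.

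Patient safety is at stake. The Contraindications section gives an increased risk of serotonin syndrome as its reason for keeping MAOIs and vortioxetine apart. Under Visit 1, a research team member judges eligibility against the inclusion and exclusion criteria, so a rule that appears only in the drug section is outside the list being applied. The trial recruits psychiatric outpatients with at least one earlier episode, and the protocol expects most to be on psychotropic medication already. Recent antidepressant changes are therefore plausible.

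**Working it through.** **1. The two rules side by side**

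| Agent | Item 16 | Contraindications | Match? |
|---|---|---|---|
| Linezolid, intravenous methylene blue | current treatment | current treatment | yes |
| MAOI for a psychiatric disorder | current treatment | current treatment, and 14 days after stopping | no |

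The gap is confined to the second row.

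**2. Can the word for current use be stretched to include a washout?** The list itself argues against this. Where a look-back is wanted it is written out: item 11 gives 6 months for ECT, and item 14 reads "Received investigational agents as part of a separate study within 30 days of the screening visit". Item 16 has no window.

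**3. Does any other step close the gap?**

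- The clinician's interaction review is worded for the current regimen. A stopped drug is not part of it.
- Screening takes a history and a count of psychotropic medications. No stop date is asked for.
- The baseline question concerns changes. A drug stopped before screening need not be reported as one.
- The antidepressant switch procedure sets no MAOI washout.
- The Week 0 physician could apply the contraindication, but no eligibility or screening text requires it.

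**4. Which stop dates are exposed?** There is no figure in the plan to reproduce, so this is a simple day count.

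- Let *s* be whole days from the last MAOI dose to screening. Item 16 is passed when *s* ≥ 1.
- Let *g* be days from screening to Day 0, taken as the first dose. The documents do not state *g*, so it is an assumption and is varied.
- Reading the 14-day window as including day 14, dosing is contraindicated when *s* + *g* ≤ 14. The exposed stop dates run from *s* = 1 to *s* = 14 − *g*, so their number is max(0, 14 − *g*).
- If day 14 itself is treated as outside the window, the condition is *s* + *g* < 14 and the number is max(0, 13 − *g*).

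| Assumed *g* (days) | Exposed stop dates, day 14 included | Exposed stop dates, day 14 excluded |
|---|---|---|
| 0 | 14 | 13 |
| 3 | 11 | 10 |
| 7 | 7 | 6 |
| 10 | 4 | 3 |
| 14 | 0 | 0 |

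The boundary convention moves the count by at most one. The schedule closes the gap only if *g* is about two weeks or more, and the protocol sets no minimum.

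**The case against.** The strongest reply is that the prohibition is already in the protocol. The Contraindications section governs dosing of the only study drug, so a site that dosed such a patient would be acting against the protocol. On this view only a repetition in the eligibility list is missing. There is also real medical oversight: Transition to Enrollment describes supervision of all MDD participants before enrolment and psychiatric monitoring during the study, and a physician sees the patient at Week 0. The screening history and chart review are not limited to current drugs and might well reveal an MAOI stopped within the past fortnight. The case report forms are not in the documents and may contain a stop-date field. The screening-only mark for eligibility is not conclusive either, since inclusion item 6 requires a MADRS threshold at baseline as well. Finally, the day count measures calendar dates, not patients or events.

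Most of this stands as mitigation. It makes a missed patient less likely and supports the view that few would be affected. It does not remove the inconsistency: the list used to admit patients accepts someone the same document says must not be dosed, and none of these safeguards requires an MAOI stop date or a 14-day check before dispensing.

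**Conclusion.** The concern holds and should be fixed. Item 16 is narrower than the protocol's own contraindication for psychiatric MAOIs; for linezolid and intravenous methylene blue the two agree. The exposed patients are those who stopped a psychiatric MAOI before screening and are still within 14 days of the last dose at Day 0.

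The mismatch is certain from the text. The number of patients is not known: it depends on an unstated MAOI frequency and an unstated screening-to-baseline interval, and is likely few. Whether such a patient would actually be missed depends on the prescriber and on forms that are not available. No endpoint, sample size or analysis is affected. The case for acting is that the potential harm is serious and the remedy costs very little.

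**What to change.** Add to item 16 a clause excluding anyone who has stopped an MAOI taken for a psychiatric disorder within the 14 days before the first dose of vortioxetine, and state whether day 14 counts. Tie the window to first dose rather than to screening, because the contraindication concerns use of the drug. At screening, record any recent MAOI use and its stop date; at baseline, check that date again before dispensing.

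The cost is one clause and one item on the screening and baseline forms. At most a few patients would be excluded or deferred, and a deferral would last no more than about 14 days.
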